### 8.5.2 Discontinuation or Withdrawal of Individual Subjects

If a subject having received the 1st prasugrel MD treatment terminates the study prematurely for any reason, all attempts should be made by the investigator to perform the procedures for the early termination visit (same as for the week 28 visit) and determine the primary reason for the termination and where possible the primary underlining reason, providing as much as detail as possible, and documenting the information on the eCRF. .

For subject who terminated before Visit 3, Platelet function tests have to be conducted during the early termination visit.

The primary reason for discontinuation or withdrawal of the subject from the study should be noted using the following categories:

- (1) Adverse Event (AE). The subject has experienced an adverse event that requires early termination because continued participation imposes an unacceptable risk to the subject's health or the subject is unwilling to continue because of the adverse event or pre-treatment adverse event.
- (2) Noncompliance with investigational medicinal product (IMP) prasugrel MD + aspirin.  
Period 1 compliance is defined as 80% compliance in the first 4 weeks with maximum 2 consecutive missed doses in the last week.  
Period 2 compliance is defined as 80% compliance in the 24 weeks (up to 12 months, alternatively)
- (3) Major protocol deviation. The subject failed to meet protocol entry criteria or did not adhere to protocol requirements, and continued participation poses an unacceptable risk to the subject's health, or a major protocol deviation occurred at the site.
- (4) Withdrawal of consent. The subject (or subject's legally acceptable representative) wishes to withdraw from the study. The reason for withdrawal, if provided, should be recorded in the case report form (eCRF). Subjects may withdraw from the study at any time at their own request without giving reasons and without any disadvantageous consequences for their subsequent medical care.
- (5) Lost to follow-up. The subject did not return to the clinic and attempts to contact the subject were unsuccessful. Attempts to contact the subject must be documented.

(6) Other.

In the case of study termination by the sponsor, institutional review board (IRB), independent ethics committee (IEC), or regulatory agency, reason for withdrawal should be captured as Other, Study Termination.

If the subject is found to be pregnant during the study, the subject must be withdrawn immediately. The reason for withdrawal should be “major protocol deviation” unless there was a complication of the pregnancy which led to withdrawal, in which case the reason for withdrawal should be “adverse event(s)”. The procedure is described in [Section 9.7](#).

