## 5.0 Introduction

### 5.1 Background

Cardiovascular diseases (CVD) are the leading cause of death in the Western world. The global number of deaths from CVD has increased during the past decade by 12.5%, with CVD now accounting for approximately one third of all deaths globally. Ischemic heart disease (IHD) is the leading component of the global CVD burden, followed by stroke and heart failure.

Platelets are an essential component of blood coagulation and are responsible for maintaining primary hemostasis under conditions of blood flow. When an arterial blood vessel is injured, platelets adhere to and aggregate at the vessel wall to initiate primary hemostasis as well as promoting secondary hemostasis to stop bleeding. In dysfunctional blood vessels (due to plaque formation, inflammation, or lipid deposition), however, platelets become activated and platelet aggregation may cause excessive thrombus formation and vascular occlusion, resulting in myocardial infarction (MI) or stroke.

Percutaneous coronary intervention (PCI), usually with stenting, has become the standard treatment for acute coronary syndromes (ACS). During this procedure, trauma commonly occurs to the arterial endothelium that, among other effects, causes the activation and aggregation of platelets. Because platelet aggregation may lead to coronary thrombosis in a patient already vulnerable to it, antiplatelet agents are essential adjunctive therapies in patients with ACS undergoing PCI. Even though stent thrombosis is a rare event, it is a severe or fatal complication and is associated with high mortality rates. The goal of antiplatelet therapy is to provide maximal protection against thrombosis without increasing the risk of bleeding. Aspirin, thienopyridines, and glycoprotein (GP) IIb/IIIa inhibitors are the mainstays of antiplatelet therapy in patients undergoing PCI. Dual antiplatelet therapy consisting of aspirin and a P2Y12 inhibitor (clopidogrel, prasugrel, or ticagrelor) is state-of-the-art therapy in ACS patients undergoing PCI for prevention of ischemic adverse events. However, a significant proportion of patients do not respond adequately to uniform antiplatelet treatment. These ‘non-responders’ have an increased risk for stent thrombosis, stroke, and other ischemic complications.

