#### **8.4.1.11 All cause deaths**

All cause deaths will be assessed at all study visits after the first prasugrel MD treatment.

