**Early Termination**

In case of an early termination after 1st prasugrel MD administration and before treatment at visit 5 (week 28), the same procedures planned for the treatment at visit 5 (week 28) should be performed.

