## 9.0 Adverse Events (AEs)

### 9.1 Definitions

#### 9.1.1 Adverse Event

An adverse event (AE) is defined as any unfavorable and unintended sign (including a clinically significant abnormal laboratory finding), symptom or disease, temporally associated with the use of a medicinal product, regardless of its nature, intensity, seriousness, or presumed relationship (causality) to the product or experimental procedure used.

Adverse Events will be collected since the informed consent signature, and all adverse events which occur after the first study medication intake and within 14 days after the treatment stop date will be considered as treatment emergent adverse events (TEAEs).

Each TEAE will be evaluated for duration, intensity, and relationship to (or association with) the study treatment (or other causes). Additionally, the actions taken (e.g., administration of treatment) and the resulting outcome of the adverse event will be indicated on the eCRF. All adverse events will be followed up until resolved or as clinically required.

Only subjects with an ongoing AE at the last study visit will be followed-up for safety reasons until the event is resolved or stabilized.

**Any AE, which remains unresolved after completion of the trial, requires detailed evaluation and follow-up until the AE has been resolved or a reasonable explanation for its persistence is found.**

If a worsening of any pathological condition that the subject had before the start of the study or medical problems that are present prior to the start of treatment but worsen during treatment occur, these must be considered as a new adverse event and will require a complete evaluation and the relevant explanation in the case report form.

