## 11.2. Determination of sample size

A total of 200 patients will be enrolled to have 170 completed patients in the study (expected drop-out rate of 15%).

The proposed total sample size of 170 completed patients will allow to estimate a mean PRU value with a precision of around 10% and a confidence level of 95%, considering a standard deviation of 70 (Han-Young Jin, 2014).

The probability that 1 or more adverse reactions (or other events) will occur in a sample of 170 patients with an anticipated incidence rate of 0.01 is 0.82%. So this sample achieves a power of 82% to find adverse events with incidences close to 0.01.

This sample size will also permit enough power to detect a statistically significant reduction of the P2Y12 ( $\neq 0$ ), considering an effect size around 0.40 ( $\mu=30$ ,  $SD=70$ ), using a significance level of 0.05 and a two-sided one-sample t-test.

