## 18.0 Appendices

### 18.1. Schedule of Assessments

← Period 1      ← Period 2      →

VISITS Week	V1 Screening	V2 Day 1	V3 Week 4	V4 Week 16	End of Study Early Termination 	
					V5 Week 28	OPTIONAL V6 Maximum 12 months of P2Y 12 inhibitor treatment after ACS underwent PCI
Study days (allowed deviation days in brackets)	D-28 to D-1	D1	D28 (± 14)	D112 (± 14)	D196 (± 28)	D365 (-28)
Informed consent	X					
Demographics	X					
Inclusion and exclusion criteria	X	X				
Medical history	X					
Physical examination	X	X	X	X	X	X
Vital signs (including blood pressure)	X	X	X	X	X	X
Pregnancy test	X				X	X
Safety laboratory tests	X	X 	X 	X 	X 	X 
Blood sample for CYP2C19 genotyping			X 			
Electrocardiogram	X		X		X	X
P2Y 12 reaction unit (PRU)		X 	X 			
HTPR		X 	X 			
Platelet inhibition (%)		X 	X 			
Major bleeding events		X	X	X	X	X
Minor and clinically relevant bleeding events		X	X	X	X	X
Major adverse cardiovascular events (MACE)		X	X	X	X	X
All cause death		X	X	X	X	X
Prasugrel Maintenance Dose (MD) + aspirin		X	X	X	X	X
Pre-treatment adverse events 	X	X 				
Treatment emergent adverse events 		X 	X	X	X 	X 
Previous medication	X					
Concomitant medication		X	X	X	X	X

- (1) Patients who signs the pharmacogenomic informed consent form separately will preserve a blood sample for CYP2C19 genotyping  
 (2) Safety lab sample to be done before prasugrel MD + aspirin administration of each corresponding visit.  
 (3) PRU to be done immediately before prasugrel MD + aspirin administration on Day 1  
 (4) PRU to be done immediately before prasugrel MD + aspirin administration on Visit 3 (Week 4)  
 (5) Adverse Events will be collected since the informed consent signature until last study visit  
 (6) Pre-treatment adverse events will be considered since signature date to the date of 1st MD prasugrel administration (until pre-dosing)  
 (7) Treatment emergent events will be considered since 1st MD prasugrel administration (post-dosing) until last MD prasugrel administration + 14 days  

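### The protocol describes no follow-up to week 28 for patients who stop prasugrel early, yet it reports 28-week bleeding, MACE and death rates in everyone dosed

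*Combined protocol and SAP*

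**What the plan says.** **Exit from the study.** Section 8.5.2 covers a treated subject who ends the study early: "all attempts should be made by the investigator to perform the procedures for the early termination visit (same as for the week 28 visit"). One list of reasons follows: "The primary reason for discontinuation or withdrawal of the subject from the study should be noted using the following categories". The list includes an adverse event, noncompliance with prasugrel plus aspirin, major protocol deviation, consent withdrawal and loss to follow-up. Under Early Termination in section 8.4.2, "the same procedures planned for the treatment at visit 5 (week 28) should be performed". The schedule in 18.1 puts early termination under the same end-of-study heading as Visits 5 and 6.

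**Collection of events.** Section 8.4.1.11 states: "All cause deaths will be assessed at all study visits after the first prasugrel MD treatment". Section 8.4.1.10 says the same of bleeding, and the 18.1 schedule ties MACE to visits. Note 5 to the schedule reads: "Adverse Events will be collected since the informed consent signature until last study visit".

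**After the last visit.** Section 9.1.1 states: "Only subjects with an ongoing AE at the last study visit will be followed-up for safety reasons until the event is resolved or stabilized". Section 9.3 follows a subject withdrawn for an AE until the outcome of that event. Section 9.1.1 and note 7 of 18.1 count events within 14 days of the last dose as treatment-emergent.

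**Analysis.** Sections 6.2.2.1 and 6.2.2.2 define 28-week incidences of major bleeding (the Period 2 primary endpoint), MACE and all-cause death, with an optional extension. Section 11.1 analyses everyone who took at least one dose. Section 11.5 plans no imputation in general. Sections 11.1.4.1.2 and 11.1.4.2.2 ask for incidences with 95% intervals, plus Kaplan-Meier median times for bleeding and MACE. Deaths are percentages. No censoring rule is given.

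**The concern.** The endpoints run to week 28 for everyone dosed, but the planned observation of a patient who leaves early ends, in general, at the early termination visit. Suppose a patient leaves at week 6 because of a bleed that then resolves, and has a stent thrombosis or dies at week 14. Week 14 is past the 14-day window, and the event is not the AE being followed. It has no planned route into the MACE or death counts, but the patient stays in the denominator.

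Leaving may well be related to risk, since an adverse event is the first reason listed. The protocol's background also treats the period after stenting as one where such events matter: "Even though stent thrombosis is a rare event, it is a severe or fatal complication and is associated with high mortality rates". At stake are the Period 2 safety rates: major bleeding, MACE and all-cause death.

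**Working it through.** **1. The plan's own figures.** Section 11.2 states: "A total of 200 patients will be enrolled to have 170 completed patients in the study (expected drop-out rate of 15" (per cent). Check: 170 / (1 − 0.15) = 200. Its detection probability also reproduces: 1 − 0.99^170 = 0.819, the stated 82%. (The same paragraph also prints this as 0.82%, a separate slip.) With all 200 followed to week 28 the probability would be 1 − 0.99^200 = 0.866.

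**2. Unobserved time.** Planned leavers: 0.15 × 200 = 30. Total planned time: 200 × 28 = 5,600 patient-weeks. With mean exit at week w (assumed), the unobserved time is 30 × (28 − w).

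| Mean exit (assumed) | Unobserved patient-weeks | Share of 5,600 |
|---|---|---|
| Week 4 | 720 | 12.9% |
| Week 14 | 420 | 7.5% |
| Week 24 | 120 | 2.1% |

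**3. Missed events in a crude rate.** Assumptions: exits spread evenly over 28 weeks (mean week 14), a constant on-treatment hazard giving 28-week risk p, and a hazard after stopping of h times that. Put x = −ln(1 − p).

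- Leaver's risk of an event before exit: 1 − p/x.
- Leaver's risk to week 28: p if h = 1; otherwise 1 − (1 − p) × [1 − exp(−(h − 1)x)] / [(h − 1)x].
- Crude rate = 0.85p + 0.15 × (risk before exit). Full rate = 0.85p + 0.15 × (risk to week 28).

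Example, p = 5% and h = 2: x = 0.05129 and p/x = 0.9748. Risk before exit is 0.0252; risk to week 28 is 1 − 0.95 × 0.9748 = 0.0739. Crude = 0.0425 + 0.0038 = 4.63%. Full = 0.0425 + 0.0111 = 5.36%. Missed: 200 × (0.0536 − 0.0463), or 1.46 events before rounding. Kaplan-Meier censored at exit would give 5.00%.

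| On-treatment risk p (assumed) | h = 1 | h = 2 | h = 5 |
|---|---|---|---|
| 1% | 0.15 events (7.5%) | 0.30 (13.9%) | 0.74 (28.5%) |
| 5% | 0.74 (7.4%) | 1.46 (13.6%) | 3.48 (27.3%) |
| 10% | 1.47 (7.4%) | 2.85 (13.3%) | 6.44 (25.8%) |

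Cells show events missed in 200 and, in brackets, their share of all events to week 28. A simple person-time version agrees: 420h / (5,180 + 420h) gives 7.5%, 14.0% and 28.8%.

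**4. What each estimator needs.** The crude rate is low whenever any event follows exit. Kaplan-Meier censored at exit is unbiased at h = 1 if exit is unrelated to risk; otherwise it estimates the risk had patients stayed on drug.

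**The case against.** Three stronger readings are tempting, and the documents do not support them.

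- *Stopping prasugrel ends participation.* Section 8.5.2 speaks of a subject who ends the study, not one who stops the drug. Section 9.4 lists drug withdrawn and dose interrupted as AE actions without tying either to exit, and section 10.1 says a deviation does not generally require withdrawal. The link is an inference from the reason list and from the absence of any other route. What stands is that the protocol does not say how such a patient is followed.
- *Later events are never collected.* The 14-day window, follow-up of ongoing AEs (9.1.1, 9.3), and the unscheduled visits and telephone contacts of section 8.4.2 can catch some. None is scheduled to look for new events up to Day 196, and the 14-day window sits badly with AE collection ending at the last visit.
- *The 28-week results are favourable by design.* For a Kaplan-Meier estimate that needs a higher risk after stopping or risk-related exit. The documents give no rate after stopping and do not say what therapy follows. Only the crude incidence is low by construction.

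The best counter-argument is that on-treatment safety is the target. The objectives concern the safety of prasugrel over its treatment period, the study has one arm, and no between-arm contrast is distorted. That is a legitimate choice, but the protocol does not state it for MACE or death: the 14-day window defines treatment-emergent AEs only. The separate SAP that section 11.1 promises could add a censoring rule, but it cannot supply events that were not collected.

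The 15% drop-out also includes consent withdrawal and loss to follow-up, so not all 30 are drug stoppers or reachable.

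**Conclusion.** The gap is real and worth closing. The protocol describes no way to stop prasugrel and stay under observation, and new major bleeding, MACE and deaths between early termination and week 28 are not systematically sought. The 28-week incidences nevertheless cover everyone dosed.

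The size is illustrative, since only the 30 of 200 comes from the documents. Between 2.1% and 12.9% of patient-weeks go unobserved for mean exit between weeks 24 and 4. With evenly spread exits and h from 1 to 5, a crude rate misses about 7% to 29% of events. At a 1% risk, the only incidence the sample-size section names, that is less than one event in 200.

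The Period 1 PRU endpoint is not affected: section 8.5.2 requires platelet function tests at early termination before Visit 3.

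**What to change.** 1. In sections 8.5.2 and 8.4.2, record stopping the study drug and withdrawing from the study as separate events, each with its own date and reason.
2. For a patient who stops the drug without withdrawing consent, keep the early termination visit and add one telephone contact at Day 196 recording vital status, MACE and major bleeding. Section 8.4.2 already foresees telephone contacts. Obtain records to confirm reported events, since a call alone may not support classifying a TIMI major bleed or an MI.
3. Report 28-week major bleeding, MACE and all-cause death for all treated subjects regardless of prasugrel status, beside on-treatment rates (to last dose plus 14 days). State the censoring rule for each.

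Cost: a protocol amendment with IRB/IEC approval, one eCRF page, at most about 30 calls, and record retrieval for reported events. A small downside is that events after stopping also reflect later therapy, which is why both rates are shown.

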## 8.6. Treatments

### 8.6.1 Treatments Administered

Subjects will be treated with prasugrel 3.75 mg once daily along with aspirin 81-100 mg per day oral dose during the study period.

The investigator’s discretion will be followed for deciding on aspirin dosing as far as continuing the dual antiplatelet therapy (DAPT) may increase the risk of gastrointestinal bleeding; therefore adverse events management related to aspirin doses will be managed as per the investigator’s criteria for this and any other criteria based on medical judgement.

Daiichi Sankyo Taiwan Ltd. will supply the IMP consisting of:

- Prasugrel 3.75 mg tablets

### 8.6.2 Identity of Investigational Product(s)

Experimental treatment:

Product Name:	Prasugrel
Drug substance:	Prasugrel hydrochloride
Pharmaceutical Form:	Tablets containing prasugrel hydrochloride 3.75 mg
Administration route:	Oral use
Dosage:	Once daily administration
Manufacturer:	Daiichi Sankyo Propharma Co., Ltd.

The IMP will be supplied as two blisters included in one medication box. The supplies will contain a surplus of tablets to cover the treatment period and visit windows. The IMP should be stored at room temperature ( $\leq 25^{\circ}\text{C}$ ).

Each box of investigational medication will be labelled with pertinent study information and country-specific regulatory caution statements in the country-specific language (Chinese).

### 8.6.3 Dosages and Regimen

Each subject who qualifies for the study will receive aspirin 81-100 mg per day and tablets of study medication: prasugrel MD 3.75 mg once daily during the study period. Subjects will receive 2 boxes of medication at Visit 2 (for 4 weeks treatment period  $\pm$  2 weeks), 4 boxes of medication at Visit 3 (for 12 weeks of treatment  $\pm$  2 weeks), 4 boxes of medication at Visit 4 (for 12 weeks of treatment  $\pm$  4 weeks), and the last 4 boxes of medication at Visit 5 (for up to maximum 12 months of treatment) for those patients proposed following investigator's discretion to the optional extension period.

Subjects will be instructed to take the tablets once daily oral dose at the same time. The first dose is to be taken the day 1 when study medication has been dispensed to the subject. Based the PRU assessment should be done immediately before the prasugrel MD + aspirin administration, the investigator will give instructions to the subject for the most appropriate timing for the daily tablets to be taken on the dates of the visits where the PRU is assessed.

The investigator's discretion will be followed for deciding on aspirin dosing as far as continuing the dual antiplatelet therapy (DAPT) may increase the risk of gastrointestinal bleeding; therefore adverse events management related to aspirin doses will be managed as per the investigator's criteria.

The investigator or designee must instruct the subject to bring each of their study medication containers (boxes) to each clinic visit, regardless of whether the study medication boxes are empty.

### 8.6.4 Packaging and Labelling

IMP manufacture will be performed according to Good Manufacturing Practice (GMP) standards and according to the currently valid version of the respective national laws applicable at Taipei, Taiwan. Identity and stability of the substance for the duration of the study are ensured and documented through Certificates of Analyses.

Products' labelling will show at least the following information:

- Name and address and contact phone of Sponsor and CRO.
- Trial reference code.
- Pharmaceutical dosage form, route of administration and quantity of dosage units.
- The number of the IMP, batch number and expiry date.
- The statement "for clinical trial use only".
- The statement "keep out of the reach of children".
- The medication number and the Patient Number.
- Storage conditions.
- Name, principal investigator.

If applicable, local or country specific requirements regarding labelling of the medication boxes are also to be considered.

### 8.6.5 Storage and Disposition of Study Drug

At each study site, the investigator is responsible for the correct storage and handling of the IMP. The IMP must be stored in a place with access limited to the investigator and/or especially authorized personnel of the local study team only, i.e. study nurse or study coordinator.

The temperature of the storage area must be monitored and documented. The investigator is required to inform the responsible monitor immediately in cases of deviation of the storage temperature from the required range (room temperature  $\leq 25^{\circ}\text{C}$ ). Furthermore adherence to the storage conditions will be checked routinely by the monitor during the on-site visits.

### 8.6.6 Method of Assigning Subjects to Treatment Groups

Not applicable as being a non-randomized study.

